## 23 APPENDIX 4 -- DETOURS DATA AND SAFETY MONITORING PLAN

Study Title: De-escalating Empiric Treatment: Opting oUt of Rx for Selected Patients with Suspected Sepsis (DETOURS)

Principal Investigator: [name], MPH

### BRIEF STUDY OVERVIEW

Sepsis has high associated mortality. Hospitals and regulatory agencies have worked to address sepsis care through core measures and bundled processes. However, important follow-up care, including re-assessments of antibiotic regimens and antibiotic de-escalation, are not strongly implemented. This study investigates the use of a novel, opt-out protocol to guide appropriate antibiotic de-escalation among those patients with suspected sepsis meeting rigorous safety checks.

### OVERSIGHT RESPONSIBILITIES

Oversight of the trial is provided by the Principal Investigator (PI), [name] and [name] (Co-Investigator). Study sites will also have Co-investigators that will help oversee local activities.

### MONITORING PROCEDURES

[name] assures that waiver of informed consent is obtained prior to performing any research procedures, that all subjects meet eligibility criteria, and that the study is conducted according to the IRB-approved research plan.

Study data are accessible at all times for the PI to review. The PI and co-investigators review study conduct: accrual, drop-outs, protocol deviations, process metrics on a monthly basis. The PI and co-investigators review(s) safety outcomes individually in real-time and in aggregate on a quarterly basis. The PI and co-investigators review(s) serious adverse events (SAEs) and any voiced complaints from clinical providers about the study protocol in real-time. The PI ensures all protocol deviations, imbalance in safety outcomes at routine assessments, and SAEs are reported to the CDC and IRB according to the applicable regulatory requirements.

### COLLECTION AND REPORTING OF SAEs AND AEs

For this study, the following standard AE definitions are used:

**Adverse event:** Any unfavorable and unintended sign (including an abnormal laboratory finding), symptom or disease temporally associated with the use of a medical treatment or

procedure, regardless of whether it is considered related to the medical treatment or procedure.

**Serious Adverse Event:** Any AE that results in any of the following outcomes:

- Death
- Life-threatening
- Event requiring inpatient hospitalization or prolongation of existing hospitalization
- Persistent or significant disability/incapacity

AEs are graded according to the following scale:

**Mild:** An experience that is transient, & requires no special treatment or intervention. The experience does not generally interfere with usual daily activities. This includes transient laboratory test alterations.

**Moderate:** An experience that is alleviated with simple therapeutic treatments. The experience impacts usual daily activities. Includes laboratory test alterations indicating injury, but without long-term risk.

**Severe:** An experience that requires therapeutic intervention. The experience interrupts usual daily activities. If hospitalization (or prolongation of hospitalization) is required for treatment it becomes an SAE.

AEs are identified by chart review after 30-days post randomization for the 30-day time period following randomization. SAEs and specific procedure-associated AEs are reported to the PI and co-investigators within 24 hours. In addition, all AEs are reported according to the Duke IRB AE reporting guidelines.

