## **5.2 Other Study Procedures**

We will enroll patients as part of this protocol but will seek a waiver of informed consent. Screening and enrollment/baseline are described above. No specific follow-up with patients will occur following hospital discharge. Therefore, the following sections are not applicable:

1. Follow-up
2. Final study visit
3. Follow-up safety phone call
4. Early termination visit
5. Unscheduled visit
6. Laboratory evaluations

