## **DATA ANALYSIS PLANS**

All randomized patients will undergo safety evaluation of the outcomes listed above.

1. Methods and timing for assessing, recording, and analyzing safety parameters – Local study personnel will be responsible for assessing and recording safety parameters within the 30-days post randomization. Duke study personnel will be responsible for monitoring safety through interaction with site PIs on a quarterly basis and with the Independent Monitor at specified schedule (Table).
2. Guidelines for determining causality or attribution –
3. Reporting procedures (for AE) – all safety parameters will be entered into the REDCap database. Site PIs will review individual AEs identified by site data entry personnel. Data on safety parameters will be provided back to study sites on a quarterly basis.

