## **Independent Monitor**

As outlined above, we believe the study intervention qualifies as quality improvement activity, and offers no additional risk than routine medical care. However, some clinicians may worry that cessation of antibiotics, even in the low risk population which DETOURS study screening processes select, could result in negative clinical outcomes for patients who had a clinically

ambiguous presentation or unconfirmed infection at the 48-96-hour time point. Thus, we plan to use an Independent Monitor for this study to both inform any divergence in safety outcomes between the intervention and control arms, and provide reassurance to participating clinicians that safety outcomes are being actively monitored during conduct of the study.

The independent Monitor will be a qualified and objective individual not directly involved with the design and conduct of the study. This individual will not be an employee of any participating institution or the study sponsor. This individual will have no conflict of interest related to assessment of the study, will have adequate experience and expertise in conduct of clinical trials, statistics, and antimicrobial stewardship.

The independent monitor will focus on safety outcomes and not the primary outcome of antibiotic use. No statistical testing alpha value will be pre-assigned to indicate the need to halt or adjust the study protocol. No hypothesis testing is planned. Instead, an expert review of patient-level outcomes will be performed to ensure no concerning differences in safety events between the two arms are emerging. Timing for review of safety data during conduct of the study will depend achievement of the following study goal enrollment milestones: 10%, 25%, 50%.

Study team statisticians will prepare the data for review by the IM on the schedule above for study-wide assessments. Outcomes of the review will be shared with Site PIs who may then pass the safety data on to clinicians for reassurance of safety monitoring. The reports will include the number and percent or median/interquartile range of safety outcomes per randomization arm as appropriate.

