## **PLAN FOR DATA MANAGEMENT**

Compliance of regulatory documents and study data accuracy and completeness will be maintained through an internal study team quality assurance process. Site PIs will assign the task of Quality Control/Quality Assurance checks to a local study monitor. To ensure the screening processes, as implemented at individual study sites, are adequately selecting the intended low-risk population for de-escalation procedures, the safety criteria will be confirmed retrospectively. The study monitor will evaluate appropriate application of the DETOURS safety check criteria for all enrolled patients at their planned 30-day post-enrollment assessment of study outcomes. This review will retrospectively confirm the presence or absence of the safety check criteria and therefor confirm fidelity to the screening protocol.

Additionally, study outcome measurement will be confirmed by requesting securely collected screenshots from the electronic health record for a random 10% sample of enrolled patients during the first month of study start at each site. The local study monitor will collect the data during their 30-day chart reviews, and the data will be reviewed by a member of the central study team to confirm the method by which outcomes are assessed. Confirmation of measurement of the primary outcome from the sampled patients will be compared to the electronic data file capture of antibiotic days for study patients.

Confidentiality throughout the trial is maintained by use of a secured data collection tools, data transfer procedures, and a plan to destroy identifiers at the earliest opportunity.

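### Appendix 4 promises real-time safety review and 24-hour SAE reporting, but the only detection method it describes is chart review after day 30; the first monitor review would lack 30-day data for roughly 40–60% of patients

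*Protocol*

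**What the plan says.** All of the following is in Appendix 4 of the protocol unless noted.

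- **Review by the investigators** (Monitoring Procedures): "The PI and co-investigators review(s) safety outcomes individually in real-time and in aggregate on a quarterly basis". The same paragraph also puts SAE review in real time.
- **Detection** (Collection and Reporting of SAEs and AEs): "AEs are identified by chart review after 30-days post randomization for the 30-day time period following randomization". That section defines an SAE as an AE with certain outcomes, so this statement covers SAEs too.
- **Reporting clock** (next sentence): "SAEs and specific procedure-associated AEs are reported to the PI and co-investigators within 24 hours". The starting point of the 24 hours is not given.
- **Recording** (Data Analysis Plans): "Local study personnel will be responsible for assessing and recording safety parameters within the 30-days post randomization".
- **Outcome assessment** (Plan for Data Management): the safety check criteria are re-verified "for all enrolled patients at their planned 30-day post-enrollment assessment of study outcomes", which again places outcome ascertainment at day 30.
- **After discharge** (main protocol, section 5.2): "No specific follow-up with patients will occur following hospital discharge".
- **Independent Monitor**: timing depends on "achievement of the following study goal enrollment milestones: 10%, 25%, 50" per cent. The monitor's table asks for number and percentage by arm without naming a denominator. No statistical boundary is set; the review is an expert reading of the observed differences.

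**The concern.** Two matters are linked.

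The first is detection. Real-time review needs events to become known as they happen. If an SAE is first identified by a chart review after day 30, a death or ICU transfer on day 2 reaches the investigators about four weeks later. No other route is described. Any informal early awareness could also differ by arm, because the study team approaches the treating teams of intervention patients and may reassess at 48 hours, whereas it has no contact over control patients.

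The second is the timing of the monitor's reviews. They fall when a given number of patients has been enrolled, whether or not those patients have finished 30 days. Recently randomised patients have no completed assessment at that point. The gap is proportionally largest at the first review, which exists to catch an early harm signal.

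The stakes are practical. With no boundary, the monitor depends entirely on the completeness of the data shown. The results go to site investigators, who may pass them to clinicians as reassurance. Section 16.2 rests the consent waiver on a minimal-risk argument, so the monitoring should work as described.

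**Working it through.** **Step 1. Set the statements side by side.** Appendix 4 gives three timings for one process: as it happens (Monitoring Procedures), within the 30 days (Data Analysis Plans), and after day 30 (Collection and Reporting). The within-30-days sentence can mean recording as events occur, or only that events inside the window count. On the first meaning it conflicts with chart review after day 30. On the second it adds no earlier route. If the 24 hours runs from the event, chart review after day 30 cannot meet it. If it runs from awareness, there is no literal clash for the clock, but real-time review remains unsupported.

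**Step 2. Reproduce the enrolment total.** Section 9.1, Table 4: one academic site at 10 per month for 15 months, two at 10 for 18 months, seven community sites at 2 for 18 months.

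10×15 + 2×(10×18) + 7×(2×18) = 150 + 360 + 252 = 762. This matches the stated target.

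**Step 3. Accrual rates.**
- Table 4, all sites open together (assumed): 3×10 + 7×2 = 44 per month.
- Synopsis, two years to complete enrolment, uniform: 762/24 = 31.75 per month.

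**Step 4. Patients past the window at each milestone.** With milestone fraction p, rate r per month and lag L days (365.25/12 = 30.44 days per month):

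completed = 762p − r × L/30.44, not below zero.

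At L = 30 and r = 44, patients still inside the window = 44 × 30/30.44 = 43.4. At r = 31.75 the figure is 31.3. Lags of 45 and 60 days assume 15 or 30 days for chart review and data entry; the protocol gives no such delay.

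| Rate per month | Lag (days) | 10% review (76.2) | 25% review (190.5) | 50% review (381) |
|---|---|---|---|---|
| 44 | 30 | 32.8 (43%) | 147.1 (77%) | 337.6 (89%) |
| 31.75 | 30 | 44.9 (59%) | 159.2 (84%) | 349.7 (92%) |
| 44 | 45 | 11.1 (15%) | 125.4 (66%) | 315.9 (83%) |
| 31.75 | 45 | 29.3 (38%) | 143.6 (75%) | 334.1 (88%) |
| 44 | 60 | 0 (0%) | 103.8 (54%) | 294.3 (77%) |
| 31.75 | 60 | 13.6 (18%) | 127.9 (67%) | 318.4 (84%) |

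Three assumed patterns of staggered site opening give 56–61% complete at the first review with a 30-day lag.

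**Step 5. Effect on a percentage.** If all enrolled patients form the denominator and those inside the window contribute no recorded events, the displayed rate is the true rate times the completed share. At the first review with a 30-day lag that is 0.43 (44 per month) or 0.59 (31.75 per month). Both conditions are assumptions; the protocol fixes neither.

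**Step 6. Readmission.** It is counted for 30 days from discharge, not from randomisation, so it can mature after day 30. The shares above are therefore upper limits for that outcome.

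**The case against.** The strongest reply is that the detection sentence does not exclude other routes. Local personnel are made responsible for safety recording, study data are open to the principal investigator at all times, and a 24-hour clock running from awareness is compatible with late chart review. This stands in part: a reader might infer that events are found only by late chart review, and the documents do not say that. They do describe no other route, and the real-time promise still lacks a mechanism.

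A reader might also infer that the early monitor reviews would be largely empty. The arithmetic does not support this. With a 30-day lag, 43–61% of patients are complete at the first review and at least 77% at the second. The second and third reviews keep a majority in every scenario tried. The first is close to empty only if an assumed delay for chart review and data entry is added.

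A further inference is that event rates would be understated by more than half. That needs fast accrual, all enrolled patients as denominator, and no events recorded from patients inside the window. The protocol leaves the denominator open.

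Finally, the review compares arms, and allocation is 1:1 within hospital. Incomplete follow-up should thin both arms alike, provided that detection does not differ by arm. The main loss is visible events, not necessarily a biased comparison. This stands.

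**Conclusion.** The inconsistency is in the text and should be resolved. Appendix 4 promises real-time review and 24-hour SAE reporting, describes detection by chart review after day 30, and elsewhere speaks of recording within the 30 days. On any reading of the clock, a serious early event could go unseen for about a month.

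The enrolment-based milestones add a limited problem. With a 30-day lag, the first review would lack completed data for roughly 40–60% of enrolled patients, the second for about 16–23%, and the third for about 8–11%. Any delay in chart review makes these worse. If all enrolled patients are the denominator, percentages would be too low in both arms, without necessarily biasing the difference between them.

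These sizes rest on the Table 4 or synopsis accrual and on assumed site-opening patterns. This is a correction that should be made. It does not show that the monitoring is without value.

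**What to change.** 1. Reconcile the Monitoring Procedures, Collection and Reporting, and Data Analysis Plans sections of Appendix 4. State which serious events are captured before day 30, by what existing route, and when the 24-hour clock starts. The route should apply equally in both arms. The eligibility census screen should not be assumed to serve: it is not described as following randomised patients, and it could not see events after discharge.
2. Keep the enrolment milestones. In the monitor's table, show the number with completed 30-day review in each arm and use it as the denominator. List separately any events already known in patients still inside the window, so that an early death or ICU transfer is not dropped.

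The cost is wording in Appendix 4 and a little more reporting work at each review.

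Triggering the reviews on completed follow-up is an option only. At 44 per month it would delay each look by about one month, and about 76.2 + 43.4 ≈ 120 patients, rather than 76, would be randomised before the first independent look.

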## MANAGEMENT OF RISKS TO SUBJECTS

### Expected AEs

Expected AEs associated with hospitalization, the receipt of antibiotics, treatment of infection and the DETOURS protocol include:

- C. difficile infection (CDI) – positive *C. difficile* stool test during the 30 days following randomization. Results from either PCR or ELISA tests are acceptable
- Clinically significant deep venous thrombosis (DVT) – diagnosis of a new DVT during the 30 days following randomization that requires anticoagulation. A radiographic finding (via ultrasound, CT, or MRI) will be required for this diagnosis.
- Readmission – return to the hospital within 30 days of hospital discharge

- Relapse of suspected sepsis – restart or escalation of antibiotic therapy coupled with repeat blood cultures (+/- 24 hours of changed in antibiotic therapy) during the 30 days following randomization.
- Acute kidney injury requiring hemodialysis – new onset acute kidney injury requiring 1 or more hemodialysis sessions during the 30 days following randomization.
- Transfer to Intensive Care Unit (ICU) – admission or transfer to any intensive care unit within 30 days of randomization.
- Death – within 30 days of randomization.
- Number of hospital days (Length of Stay) starting on the day of randomization and up to 30 days post randomization.
- Re-initiation of antibiotic therapy after >48 hours of no antibiotics within 30 days of randomization.
- Need for new PICC line insertion within the 30 days of randomization.

Causality of SAEs to the study protocol will not be assessed, as the study monitoring plan follows global patient outcomes due to antibiotic exposures. Thus, effects from routine care and the study protocol are difficult to attribute because this is a quality improvement protocol.

## **DATA ANALYSIS PLANS**

All randomized patients will undergo safety evaluation of the outcomes listed above.

1. Methods and timing for assessing, recording, and analyzing safety parameters – Local study personnel will be responsible for assessing and recording safety parameters within the 30-days post randomization. Duke study personnel will be responsible for monitoring safety through interaction with site PIs on a quarterly basis and with the Independent Monitor at specified schedule (Table).
2. Guidelines for determining causality or attribution –
3. Reporting procedures (for AE) – all safety parameters will be entered into the REDCap database. Site PIs will review individual AEs identified by site data entry personnel. Data on safety parameters will be provided back to study sites on a quarterly basis.

## **Independent Monitor**

As outlined above, we believe the study intervention qualifies as quality improvement activity, and offers no additional risk than routine medical care. However, some clinicians may worry that cessation of antibiotics, even in the low risk population which DETOURS study screening processes select, could result in negative clinical outcomes for patients who had a clinically

ambiguous presentation or unconfirmed infection at the 48-96-hour time point. Thus, we plan to use an Independent Monitor for this study to both inform any divergence in safety outcomes between the intervention and control arms, and provide reassurance to participating clinicians that safety outcomes are being actively monitored during conduct of the study.

The independent Monitor will be a qualified and objective individual not directly involved with the design and conduct of the study. This individual will not be an employee of any participating institution or the study sponsor. This individual will have no conflict of interest related to assessment of the study, will have adequate experience and expertise in conduct of clinical trials, statistics, and antimicrobial stewardship.

The independent monitor will focus on safety outcomes and not the primary outcome of antibiotic use. No statistical testing alpha value will be pre-assigned to indicate the need to halt or adjust the study protocol. No hypothesis testing is planned. Instead, an expert review of patient-level outcomes will be performed to ensure no concerning differences in safety events between the two arms are emerging. Timing for review of safety data during conduct of the study will depend achievement of the following study goal enrollment milestones: 10%, 25%, 50%.

Study team statisticians will prepare the data for review by the IM on the schedule above for study-wide assessments. Outcomes of the review will be shared with Site PIs who may then pass the safety data on to clinicians for reassurance of safety monitoring. The reports will include the number and percent or median/interquartile range of safety outcomes per randomization arm as appropriate.

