The study involves the implementation of prompts and guidance for de-escalation decisions to prevent adverse outcomes among patients with suspected sepsis and broad spectrum antibiotic exposures. We do not believe the opt-out protocol intervention will lead to additional risk for the patient. In fact, we believe that the patients participating in the study will be more likely to improved care and outcomes because of the study. One potential risk is that antibiotics might be inappropriately stopped in patients who are, in-fact, at risk of sepsis or have a clinical infection that requires antibiotic therapy. First, this risk has been thoroughly and carefully considered in design of the opt-out protocol itself and a rigorous safety check prior to employing the opt-out procedure. A 10-month protocol development process was undertaken by the DETOURS expert panel, that included CDC experts as well as academic and clinical experts in sepsis and infectious diseases at CDC Prevention Epicenters, Duke, and DASON sites. A modified Delphi approach with four rounds of electronic surveys and multiple interim web/phone conferences resulted in development of the current list of safety screen checklist factors to adequately exclude at-risk patients and better identify appropriate patients for antibiotic de-escalation. Second, as part of the “opt-out” mechanism for the protocol, the treating provider maintains autonomy and responsibility for antibiotic treatment decisions at all times. Thus, although the protocol is offered as a decision support tool, the ultimate decision-making still remains with the treating provider. Like other persuasive antimicrobial stewardship interventions (e.g. post-prescription review and feedback), we believe this intervention qualifies as a quality improvement activity that provides support for decision-making rather than removing autonomy from prescribers. See Section 16 for additional information regarding why we believe this study is a minimal risk study.

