#### **Endpoints**

*Primary endpoint:*

- 1) Antibiotic utilization measured as antibacterial Days of Therapy (DOT) among randomized patients.
  - a. Definitions
    - i. Days of therapy (DOT) is defined as the number of calendar days of antibacterial agent exposure. A DOT is counted for any amount of antimicrobial given on that calendar day. For example, administration of cefazolin as a single dose or as 3 doses given 8 hours apart but within the same 24-hour period both represent 1 DOT. Single agents are counted separately and then summed. For example, administration of vancomycin plus ceftazidime on the same calendar day would represent 2 DOT for the same calendar day.
    - ii. Antibacterial agents will be defined by NHSN AU Module antimicrobial category="Antibacterial" (see Appendix 3). Antibiotics added to the NHSN AU option during the study (e.g. if newly FDA-approved), will be added to the study protocol Table as needed.
      1. "Luminal" antibiotics that do not achieve adequate distribution for treatment of systemic infections will be excluded as follows: oral vancomycin, fidaxomicin, and rifaxamin.
      2. Route of antibacterials will be limited to those identified in the NHSN AU module given by digestive, intravenous, inhaled, or intramuscular.
  - b. Measurement of DOT will start one day after randomization to ensure antibacterial agents given prior to randomization are not included in outcome.
  - c. Measurement will include inpatient DOT plus intended post-discharge antibacterial DOT through 30 days post-randomization.
    - i. Post-discharge antibacterial DOT will be limited to the planned DOT/duration at the time of discharge
    - ii. DOT associated with readmissions during the 30-day post-randomization period will not be included in the primary endpoint, but will be included in measurement of adverse events.

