**Table for Review by the Internal Monitor**

	Intervention	Control	Total
C. difficile infection, No. (%)			
Deep venous thrombosis, No. (%)			
Readmission, No. (%)			
Sepsis relapse, No. (%)			
Acute kidney injury requiring hemodialysis, No. (%)			
ICU transfer, No. (%)			
Death, No. (%)			
Hospital days (Length of stay), median, interquartile range			
Re-initiation of antibiotic therapy, No. (%)			
New PICC line insertion, No. (%)			

Communication plans for interaction between the IM and the study team will be primarily through email. The IM will respond with 7 business days of receipt of the safety data report with

their assessment. If further discussion is needed, then phone discussion within 3 business days will be arranged.

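### Appendix 4 allows by-arm interim safety figures to reach site PIs and, at their discretion, the treating clinicians whose decisions produce the primary outcome.

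*Protocol*

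**What the plan says.** Under Independent Monitor, Appendix 4 ties the reviews to "enrollment milestones: 10%, 25%, 50" per cent of the goal, so all three fall while patients are still being randomized. On content it says: "The reports will include the number and percent or median/interquartile range of safety outcomes per randomization arm as appropriate". The layout headed "Table for Review by the Internal Monitor" has Intervention, Control and Total columns for nine yes/no outcomes (including death, ICU transfer, sepsis relapse and re-initiation of antibiotics) plus length of stay.

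On release it says: "Outcomes of the review will be shared with Site PIs who may then pass the safety data on to clinicians", the stated aim being reassurance. No numerical guide is set for reading a difference: "No statistical testing alpha value will be pre-assigned to indicate the need to halt or adjust the study protocol".

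A second channel appears under Data Analysis Plans in the same appendix: "Data on safety parameters will be provided back to study sites on a quarterly basis". It does not say whether these data are split by arm.

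The primary endpoint (Section 5.1) is "Antibiotic utilization measured as antibacterial Days of Therapy (DOT) among randomized patients". Section 2.3.1 states that "the treating provider maintains autonomy and responsibility for antibiotic treatment decisions at all times".

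**The concern.** In this trial the people who may receive the interim comparison are the people whose behaviour is being measured. In the intervention arm the prescriber accepts or declines the stop. In the control arm the prescriber alone sets the duration. Randomization is by individual patient, stratified by hospital (Section 9.2), so one prescriber can treat patients in both arms. Section 10 already lists as a limitation that a prescriber may carry what is learned from an intervention patient over to a control.

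Circulating by-arm results adds another route to the same problem. An apparent excess of relapses or ICU transfers could raise opt-outs for the rest of enrolment. An apparent benefit could spread de-escalation to controls. Either would change the contrast in DOT that the trial is meant to estimate. At the early looks, much of any visible difference could be chance.

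**Working it through.** The plan gives no figure on this point, so there is none to reproduce. The question is how often a by-arm table would look imbalanced when the arms do not differ.

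**Inputs**
- Target enrolment 762 (Section 9.1), allocation 1:1 (Section 9.2), looks at 10%, 25% and 50% (Appendix 4).
- Patients at each look: 0.10 × 762 ≈ 76, 0.25 × 762 ≈ 190, 0.50 × 762 = 381. Per arm: about 38, 95 and 190.
- Event rate p, equal in both arms. The protocol states no safety event rates, so p is an assumption: 5% as the central case, with 2%, 10% and 20% as the range.

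**Method.** The event counts X and Y in the two arms are independent Binomial(n, p). The chance of an apparent doubling is the sum of P(X = x)·P(Y = y) over all unequal pairs in which the larger count is at least twice the smaller. The 95% half-width for the risk difference is 1.96·√(2p(1−p)/n).

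**Half-width at p = 5%**
- n = 38: 1.96·√(2 × 0.05 × 0.95 / 38) = 9.8 points
- n = 95: 6.2 points
- n = 190: 4.4 points

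**Chance of an apparent doubling with no true difference, p = 5%**

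| Look | Per arm | Expected events per arm | One arm at least double the other |
|---|---|---|---|
| 10% | 38 | 1.9 | 64% |
| 25% | 95 | 4.8 | 37% |
| 50% | 190 | 9.5 | 17% |

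**Sensitivity to p at the first look (38 per arm):** 63% at 2%, 64% at 5%, 43% at 10%, 19% at 20%.

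**How much is trivial splits.** At 38 per arm and p = 5%, about 32 of the 64 percentage points come from splits of 0 v 1, 0 v 2 or 1 v 2 events. If the larger arm must have at least two events, the chance is still 56%.

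These figures are for a single outcome. The table has nine yes/no outcomes, so an imbalance somewhere in it is more likely than in any one row.

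**What the arithmetic does not show.** It describes noise in the tables. It does not say how prescribers would react, and nothing in the protocol allows that to be derived.

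**The case against.** The strongest reply is that sharing is deliberate. Appendix 4 gives the monitor two purposes: to detect divergence between arms, and to reassure participating clinicians that safety is being watched. The intervention is delivered through clinicians, and study personnel are not blinded after randomization (Section 5.1, Blinding). What site PIs receive is called the outcomes of the review, which can mean the monitor's assessment alone; the sentence on by-arm content may describe only the report sent to the monitor. DOT is not in the table. Noise also falls as enrolment grows.

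Much of this stands as a limit on the point. A reader might infer that prescribers will see by-arm comparisons. The text does not support that, because onward release is optional and its content is partly ambiguous. A reader might also take the quarterly feedback as a second by-arm leak; the protocol does not say that it is by arm. Nor can one infer that the DOT effect will be biased by a given amount or in a given direction. And confining by-arm tables to the monitor and the preparing statistician alone would conflict with the rest of the protocol. In Appendix 4, Monitoring Procedures, the PI and co-investigators review aggregate safety quarterly and the PI reports imbalances to the CDC and IRB. Section 7 has the monitor's data discussed with the central study team.

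The reply does not remove the point. The release sentence refers to the safety data being passed on, and the next sentence describes reports by arm, so the natural reading allows figures to travel. Knowing one patient's assignment is different from seeing the pooled comparison. Relapse, ICU transfer and antibiotic re-initiation are likely to bear on a decision to stop or continue. The stated aim, reassurance that monitoring is active, is met by the monitor's conclusion without the figures.

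**Conclusion.** The concern holds as a permitted and avoidable exposure. The wording allows by-arm interim safety results to reach site PIs and, at their discretion, the clinicians whose choices in both arms make up the primary outcome. At the first look such a table would often mislead: an apparent doubling arises by chance with probability 19% to 64% over assumed event rates of 2% to 20%. At a 5% rate the probability falls to 37% and then 17% at the later looks. These figures rest on assumed rates, equal true risk and one outcome at a time. The effect on opt-out rates, control prescribing or DOT is of unknown size and direction. This is a cheap improvement to the conduct of the trial. It is not an error in the analysis, and it leaves the planned 762 patients and the stated 87% power unchanged.

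**What to change.** - **Appendix 4, Independent Monitor:** state that, until enrolment ends, site PIs and treating clinicians receive only the monitor's written recommendation (for example continue, modify or pause) and no by-arm figures.
- **Appendix 4, Data Analysis Plans:** state that quarterly safety feedback to sites is pooled over arms.
- **Section 7 and Appendix 4, Monitoring Procedures:** name which central-team members may see by-arm aggregates for the required CDC and IRB reporting, and state that they do not pass them to sites. Say how this applies to site co-investigators, since Monitoring Procedures gives co-investigators the quarterly aggregate review.
- Leave real-time handling of individual serious events as written.

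The cost is a few sentences in these places, with no change to sample size, power or analysis. The downside is that clinicians are reassured by the monitor's statement rather than by numbers.
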